#### **10.5. SAFETY ANALYSIS**

Adverse events reported on case report forms will be mapped to preferred terms and organ systems using the MedDRA mapping system. Vital signs and clinical laboratory results will be descriptively summarized in terms of change from screening values.

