### 4. SUMMARY OF STUDY DESIGN

This is a Phase I, single center, randomized, double-blind, placebo-controlled, SAD study of three escalating doses of PTI-125 in healthy male and female volunteers, 18-45 years of age. A total of twenty-four (24) subjects will be enrolled into the study in one of three dose cohorts. Each cohort will contain 8 subjects; six (6) subjects will receive PTI-125 and two (2) will receive placebo in each cohort. Three single ascending doses of PTI-125 oral solution (50, 100, and 200 mg) or placebo solution will be administered to respective cohorts.

The study includes a screening period (Day -28 to Day -1) and an inpatient treatment period (Day 0 through Day 4) and a follow-up visit (Day 7). Subjects will report to clinic the day before dosing and will be randomized to receive either a single dose of orally administered PTI-125 or placebo. Each dose will be administered following an overnight fast of 10 h.

For each dose level, dosing will be staggered such that 2 subjects (one active and one placebo) will be dosed prior to the rest of the group. After a minimum of 24 h and review of all 24-h safety assessments (ECG, brief physical, vital signs and laboratory

---

 Guidance for Industry: Estimating the Maximum Safe Starting Dose in Initial Clinical Trials for Therapeutics in Adult Healthy Volunteers. FDA, CDER, July 2005.

assessments) an independent Data Safety Monitoring Board/Data Monitoring Committee (DSMB/DMC) will determine whether the remaining 6 subjects will be dosed. If safety concerns are raised, 2 additional subjects (randomized according to the Rand schedule to maintain blinding) will be dosed followed by collection and review of the 24-hour safety assessments. The DSMB/DMC will determine after review if dosing will proceed for the remaining 4 subjects.

PK blood samples will be obtained prior to dosing and at specified intervals during the study (0-72 h post-dose). PK parameters will be calculated using non-compartmental analysis.

Blood draws for laboratory testing will be performed prior to dosing and at 24 h post-dose. After safety assessments of ECG, vital signs and a brief physical exam at 72 h, subjects will be discharged from the clinic and will return 7 days post-dose for a final safety assessment.

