## **6.3. CONCOMITANT MEDICATIONS**

Use of prescription medications will be prohibited for 14 days before initial drug administration and during the study. Non-prescription medications will be prohibited for 48 h before initial drug administration and during the study.

Use of alcohol and caffeine- or xanthine-containing products is prohibited for all subjects 48 h before dosing and during the study.

Use of grapefruit, grapefruit juice, and grapefruit-containing products is prohibited for all subjects 7 days before dosing and during the study.

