### **7.1. EVALUATIONS BY VISIT**

#### **7.1.1. *Screening Period***

The following will be completed within 29 days prior to administration of the study medication:

- Informed Consent (written consent must be obtained prior to conducting any screening activities)
- Review of Inclusion and Exclusion Criteria

- Medical history
- Review of concomitant medications
- Physical examination, including measurement of orthostatic vital signs (blood pressure, temperature, pulse and respiratory rate after a 3-min sitting period followed by blood pressure and pulse after a 2-min stand period), height, weight and calculated BMI.
- A 12-lead ECG (5-minute supine)
- Laboratory assessments, including serum chemistry, hematology, and urinalysis; ethanol breath test, urine drug screen, urine cotinine, HIV test, HBsAg and HCV Antibody.
  
- FSH test for female subjects claiming post-menopausal status

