#### 7.1.2. *In-patient Period - Study Days 0-4*

**Note:** Study Day 1 is defined as the day of dosing for each dose cohort.

Subjects will check into the clinic at the designated time on Day 0, and will remain confined to the clinic until Study Day 4. Upon check-in, the following assessments will be conducted:

- Confirmation of inclusion/exclusion criteria
- Ethanol breath test
- Urine drug screen
- Urine Cotinine test
- Review of concomitant medications
- Orthostatic vital signs (blood pressure, temperature, pulse and respiratory rate after a 3-min sitting period followed by blood pressure and pulse after a 2-min stand period).
- Brief physical examination

Following a supervised fast for at least 10 h, subjects will be administered a single oral dose of study drug (or placebo) on Study Day 1.

The appropriate dosing syringe of PTI-125 or placebo (15 ml ORA-sweet SF mixed with 1, 2 or 4 ml pH 5.2, 0.3 M citric acid / citrate buffer) mixed with ORA-sweet SF for taste masking will be administered. Subjects will also consume water provided as a rinse of the dosing syringe, to ensure complete consumption of study drug.

No food will be allowed for 4 h post-dose. Water will be allowed as desired except for 1 h before and 1 h after dosing. At 4 h post-dose, subjects will be provided a standard lunch.

On the morning of Study Day 1, within 30 min prior to dosing, the following assessments will be conducted:

- Orthostatic vital signs (blood pressure, temperature, pulse and respiratory rate after a 3-min sitting period followed by blood pressure and pulse after a 2-min stand period).
- Review of concomitant medications
- Blood sample collection for baseline PK assessment (Sample Time=0)
- On Day 1, blood sample collection for laboratory testing prior to dosing (Time=0)
- ECG (Time=0)

After dose, the following assessments will be conducted:

- Orthostatic vital signs (blood pressure, temperature, pulse and respiratory rate after a 3-min sitting period followed by blood pressure and pulse after a 2-min stand period) at approximately 10 and 30 minutes, and 1, 2, 3, 4, 8, 12, 24, 36, 48 and 72 h post-dose.
- Blood samples will be drawn at 20, 40, and 60 min following dosing and at 2, 3, 4, 6, 8, 12, 24, 36, 48 and 72 h for PK assessments
- Adverse event monitoring
- Clinical laboratory tests at approximately 24 h post-dose
- Brief physical examination at approximately 24 and 72 h post-dose

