## 7.2. LABORATORY ASSESSMENTS

### 7.2.1. *Clinical Laboratory Tests*

The following clinical laboratory tests will be performed at screening, Day 1 pre-dose, at 24 h post-dose, and at the Day 7 follow-up visit:

- Hematology: white blood cell (WBC) count with differential, red blood cell (RBC) count, hemoglobin, hematocrit, platelet count.
- Serum Chemistry: glucose, sodium, potassium, chloride, bicarbonate, blood urea nitrogen (BUN), creatinine, uric acid, phosphorus, calcium, total protein, albumin, globulin, alkaline phosphatase, alanine transaminase (ALT), aspartate transaminase (AST), gamma glutamyl transpeptidase (GGT), total bilirubin, lactose dehydrogenase (LDH).
- Urinalysis: color, specific gravity, pH, protein, sugar, ketones, occult blood, creatinine clearance calculation by Cockcroft-Gault equation.
- At screen only: FSH will be performed on all females claiming to be of post-menopausal status.

The following tests will be performed at screening and at check-in to the clinic:

- Urine drug screen: amphetamines, barbiturates, benzodiazepines, cocaine, opiates, and cannabinoids
- Urine Cotinine
- Ethanol breath test
- HIV test (screening only)
- HBsAg, HCV Antibody tests (screening only)

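### Section 10.5 measures safety change from screening, 2 to 29 days before dosing, although a Day 1 pre-dose value is collected; drift before dosing therefore enters each group's change

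*Combined protocol and SAP*

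**What the plan says.** The analysis rule is one sentence in Section 10.5: "Vital signs and clinical laboratory results will be descriptively summarized in terms of change from screening values".

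The timing of screening comes from two places. Section 4 says: "The study includes a screening period (Day -28 to Day -1) and an inpatient treatment period". Section 7.1.1 says: "The following will be completed within 29 days prior to administration of the study medication". Section 7.1.2 puts check-in on Day 0 and dosing on Day 1.

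Both kinds of measurement are repeated shortly before dosing:

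- **Vital signs.** They are taken at check-in and again on Day 1. Section 7.1.2 introduces the Day 1 list with "On the morning of Study Day 1, within 30 min prior to dosing, the following assessments will be conducted", and orthostatic vital signs are its first item.
- **Laboratory tests.** Section 7.2.1 says: "The following clinical laboratory tests will be performed at screening, Day 1 pre-dose, at 24 h post-dose, and at the Day 7 follow-up visit". Section 7.1.2 and the Appendix A schedule agree.

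Section 7.1.2 calls the Time=0 PK sample the baseline PK sample. No section gives the Time=0 safety measurements that role, and none explains the choice of screening.

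**The concern.** The change the reader wants runs from just before dosing to after dosing. The change Section 10.5 specifies starts up to 29 days earlier, before admission to the unit, and so also contains whatever happened in between.

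Conditions at screening can differ from those at Time=0 in ways the protocol itself creates. Section 6.3 says "Use of alcohol and caffeine- or xanthine-containing products is prohibited for all subjects 48 h before dosing and during the study" and "Use of prescription medications will be prohibited for 14 days before initial drug administration and during the study", and most possible screening days fall before those restrictions begin. The Day 1 sample follows a supervised fast of at least 10 h, whereas Section 7.1.1 states no fast for the screening laboratory tests, which include glucose. Exclusion criterion 14 allows one repeat of AST/ALT or total bilirubin, so a subject may have two screening values, and Section 10.5 does not say which one is the reference.

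Safety is part of the study objective (Section 3). The introduction reports raised blood pressure in high-dose female dogs and sporadic clinical chemistry changes at the high dose, which are the kinds of measure these tables summarise. With 6 active and 2 placebo subjects per cohort, a within-group shift is easy to misread.

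**Working it through.** **1. Age of the reference value.** For screening on Day k and dosing on Day 1, with a Day 0 in between, the gap is 1 - k days.

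- k = -28: 1 - (-28) = 29 days. This reproduces the 29 days in Section 7.1.1.
- k = -1: 1 - (-1) = 2 days.

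With the Day 1 value as reference, the gap for vital signs is at most 30 minutes, and the laboratory reference is the Time=0 sample.

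**2. Screening days that precede the Section 6.3 restrictions.**

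- Gap above 2 days (48 h, alcohol and caffeine): Day -28 to Day -2, which is 27 of 28 days.
- Gap above 14 days (prescription medicines): Day -28 to Day -14, which is 15 of 28 days.

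These count possible days. They do not forecast when subjects are screened.

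**3. How drift enters.** For each subject,

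(post - screening) = (post - pre-dose) + (pre-dose - screening).

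Taking group means, the mean of the last term enters the summarised change with coefficient 1. It arises before dosing, so it cannot be a drug effect.

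**4. Time points affected.** All of them use the screening reference. Vital signs have 12 in-unit post-dose times (10 and 30 min; 1, 2, 3, 4, 8, 12, 24, 36, 48 and 72 h) plus Day 7, so 12 of 13 fall in the same stay as Time=0. Laboratory tests have 24 h and Day 7, so 1 of 2 does.

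**5. Precision (illustration only).** The documents give no SD or correlation. With equal variances at each time and correlation r between reference and post-dose value, SD of change = SD × sqrt(2(1 - r)). The ratio of the two SDs is sqrt((1 - r_screen)/(1 - r_pre)). Assume r_screen of 0.4 to 0.7 and r_pre of 0.7 to 0.9:

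- smallest ratio: sqrt(0.3/0.3) = 1.00
- largest ratio: sqrt(0.6/0.1) = 2.45

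For an active-versus-placebo contrast with 6 active subjects, SE = sqrt(1/6 + 1/n_placebo) × sqrt(2(1 - r)), in units of the between-subject SD:

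| Placebo subjects | r = 0.5 (screening) | r = 0.8 (pre-dose) |
|---|---|---|
| 2 (own cohort) | 0.816 × 1.000 = 0.82 | 0.816 × 0.632 = 0.52 |
| 6 (pooled) | 0.577 × 1.000 = 0.58 | 0.577 × 0.632 = 0.37 |

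**6. One source of drift that can be sized under assumptions.** Exclusion criterion 14 caps AST/ALT and total bilirubin at the ULN. If the screening value is the qualifying one and values are normal, regression to the mean raises later values by (1 - r) × φ(c)/Φ(c) SD on average. Here c is the ULN in SD units and r the correlation between screening and later values. With c assumed at 1.645 to 1.96 and r at 0.5 to 0.9, this is about 0.01 to 0.05 SD. It is small, but it is upward in every group.

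**The case against.** The strongest reply is that the harm may be visible and reversible. Section 10.5 lists no time points and does not exclude Time=0. If the tables carry a Time=0 row, that row shows the mean drift. With complete data, subtracting it from a later row gives the mean change from pre-dose exactly, and only the SD would need recalculating. This is fair, and nothing is lost for good. But it depends on a table layout the plan does not specify, and it leaves the reader to undo the stated analysis.

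Further objections, and what stands of each:

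- **No drift size is given, and the correlations are assumed.** This stands. The assumed ranges meet only at 0.7, so they leave out any case where pre-dose is the noisier reference. Under equal variances that would require screening to correlate better with post-dose values than pre-dose does. Section 10.5 also specifies no active-versus-placebo contrast. The SD and SE figures therefore deserve little weight, but the drift argument in step 3 does not depend on them.
- **The day counts show opportunity, not effect.** This also stands. Subjects are healthy and are tested for ethanol and drugs at both screening and check-in, and nothing shows that they used restricted products at screening.
- **Change from Time=0 is not a pure drug effect either.** Correct. Confinement, meals and time of day still differ between Time=0 and later times, and placebo is still needed for interpretation. The gain may be smaller for the outpatient Day 7 laboratory tests.
- **No decision depends on these tables.** Largely right. The limits for AST/ALT, bilirubin and creatinine in Section 4.1 are multiples of the ULN, and the DSMB/DMC reviews the 24 h assessments directly.

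These points limit the severity. None gives a reason to prefer screening as the reference.

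**Conclusion.** The concern holds. Section 10.5 sets a reference that is 2 to 29 days old when a value taken just before dosing is already scheduled, so mean drift before dosing passes in full into each group's summarised change. The window, the day counts and the identity follow from the documents alone. The size of the drift and any gain in precision do not: the SD ratio of 1.00 to 2.45 rests on assumed correlations and equal variances, and at 1.00 only the drift is removed.

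Randomised placebo subjects share the expected drift, so an active-versus-placebo contrast is not biased. It is noisier if screening correlates less with post-dose values than pre-dose does, and with 2 placebo subjects per cohort (6 pooled) the drift cancels only in expectation. Stopping rules, alpha and power are unaffected. The point should be fixed because it concerns a stated objective and costs almost nothing; it does not threaten the trial.

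**What to change.** In Section 10.5:

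- Define baseline for vital signs and laboratory tests as the last value before dosing, normally Day 1, Time=0.
- State the fallback if that value is missing: the check-in value for vital signs, otherwise the screening value. If a screening test was repeated, the last result applies.
- Summarise change from that baseline at each post-dose time, and show screening values separately so that any drift can be seen.

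The cost is two or three sentences. No new visits, samples or data are needed.

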### **7.1.3. Follow-up Visit – Study Day 7**

At the Day 7 follow up visit, the following assessments will be conducted:

- Orthostatic vital signs (blood pressure, temperature, pulse and

respiratory rate after a 3-min sitting period followed by blood pressure and pulse after a 2-min stand period)

- ECG
- Adverse event monitoring
- Physical examination
- Clinical laboratory tests

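### Sitting and standing readings are paired on 16 occasions per subject, but Section 10.5 plans only change from screening, so the spread of the postural change and the number of subjects with a postural fall are not reported

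*Combined protocol and SAP*

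**What the plan says.** Every set of vital signs in this protocol includes a sit-to-stand procedure. Readings are taken after three minutes seated, "followed by blood pressure and pulse after a 2-min stand period".

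The sets are scheduled as follows:
- Screening (Section 7.1.1): "Physical examination, including measurement of orthostatic vital signs".
- Check-in on Day 0 and again before dosing on Day 1 (Section 7.1.2). The pre-dose list opens "On the morning of Study Day 1, within 30 min prior to dosing, the following assessments will be conducted", and orthostatic vital signs are its first item.
- After dosing (Section 7.1.2): "at approximately 10 and 30 minutes, and 1, 2, 3, 4, 8, 12, 24, 36, 48 and 72 h post-dose".
- Day 7 (Section 7.1.3), where orthostatic vital signs are on the list of follow-up assessments.

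The analysis of all these readings is one sentence in Section 10.5: "Vital signs and clinical laboratory results will be descriptively summarized in terms of change from screening values". It does not say whether sitting values, standing values or both are summarised, or which statistics are used. No section defines a standing-minus-sitting difference, a postural threshold, a count of subjects with a fall, or an individual listing. The stopping criteria in Section 4.1 contain graded signs and symptoms and laboratory limits, but no blood pressure or postural limit.

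**The concern.** Measuring the same subject seated and then standing a few minutes later yields a difference within that subject and occasion. The planned analysis instead compares each reading with the one taken at screening. Followed as written, it produces no postural difference, although the data for one are collected throughout.

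Safety is a stated objective (Section 3) of a first-in-human study with six active subjects per dose. At that size an effect on posture could well appear as a clear fall in one or two subjects. A group summary of change from screening shows that pattern poorly, whereas a count of affected subjects shows it directly. If the definition is left until the data are in hand, any cut-off chosen then carries less weight than one stated beforehand.

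**Working it through.** The plan gives no figure to reproduce here, so the check is a count followed by two illustrations.

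**1. Occasions per completing subject** (Sections 7.1.1 to 7.1.3)

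Post-dose in-patient times: 10 and 30 min, then 1, 2, 3, 4, 8, 12, 24, 36, 48 and 72 h, which is 12.

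Screening 1 + check-in 1 + pre-dose 1 + post-dose 12 + Day 7 1 = **16**, of which 12 + 1 = **13** follow dosing. Sets taken at early discontinuation (Section 8) are not counted.

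**2. Post-dose pairs** (Section 4: three cohorts, each with 6 active and 2 placebo)

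- All subjects: 24 × 13 = **312**
- Active subjects: 18 × 13 = **234**

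**3. Effect of one subject on a cohort mean**

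Shift in the mean = fall / n, with n = 6. The falls are assumed; the documents give none.

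| Assumed standing fall in one subject | Shift in mean standing change | Count |
|---|---|---|
| 20 mmHg | 20/6 = 3.3 mmHg | 1 of 6 |
| 30 mmHg | 30/6 = 5.0 mmHg | 1 of 6 |
| 40 mmHg | 40/6 = 6.7 mmHg | 1 of 6 |

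**4. Chance that at least one of six active subjects is affected**

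1 − (1 − p)^6, with p assumed:
- p = 10%: 1 − 0.9^6 = 47%
- p = 20%: 1 − 0.8^6 = 74%

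**5. What separate sitting and standing summaries can and cannot show**

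For complete pairs, mean standing change minus mean sitting change equals the mean change in the postural difference. The mean is therefore recoverable. The spread is not, because it depends on the covariance of the two positions. The count is not, because it depends on which readings belong to the same subject.

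Take two assumed cohorts of six, with changes from reference in mmHg:
- Cohort A: one subject falls 30 sitting and 30 standing; the other five do not change.
- Cohort B: one subject falls 30 sitting only, another falls 30 standing only; the other four do not change.

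| | Cohort A | Cohort B |
|---|---|---|
| Sitting change: mean, minimum | −5, −30 | −5, −30 |
| Standing change: mean, minimum | −5, −30 | −5, −30 |
| Mean change in standing minus sitting | 0 | 0 |
| SD of that change | 0 | √[(30² + 30²)/5] = 19.0 |
| Subjects whose postural difference falls by 30 | 0 of 6 | 1 of 6 |

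Every separate summary of the two positions, including the extremes, is identical in the two cohorts. Only the paired difference tells them apart.

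**The case against.** Several points on the other side stand.

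- **Purpose.** A reader might infer that the trial set out to measure orthostatic intolerance. Section 3 states only safety and pharmacokinetics in general, and the protocol uses the orthostatic label for its whole vital-signs set, including temperature and respiratory rate. The nonclinical summary in Section 2 reports no adverse blood pressure effect in the dog cardiovascular study; the pressure finding it does report is an increase in high-dose female dogs. The value of the postural difference is inferred from the repeated procedure, not from a named endpoint.
- **Silence is not exclusion.** A reader might infer that no postural information would be reported at all. Section 10.5 does not rule out a derived difference. The mean shift is recoverable if both positions are tabulated. A minimum by time point could also expose one extreme standing change, so the 5 mmHg figure describes the mean and not every possible descriptive statistic. As the two cohorts above show, a minimum still does not give the paired difference.
- **Other routes.** A reader might infer that individual falls are lost to the trial. Under Section 9.1 a new clinically significant abnormality in physiological testing is an adverse event. The DSMB/DMC reviews 24-hour vital signs in the sentinel subjects (Section 4), and safety results are reviewed before discharge (Section 7.1.2). These are real safeguards. They rest on judgment, set no postural criterion, and do not give a tabulation across all subjects.
- **Reference value.** A reader might infer that a postural difference needs no baseline, because each occasion is its own control. It does need one: without a pre-dose reference, a subject's habitual postural drop could be taken for a drug effect.

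**Conclusion.** The point holds as a gap in the analysis plan. Each completing subject contributes 13 post-dose sitting and standing pairs, and the one planned summary does not use the pairing. Two things are therefore missing: the spread of the postural change, and the number of subjects with a postural fall. The count of 16 occasions is exact for a subject who completes the schedule. The 3.3 to 6.7 mmHg range and the 47% and 74% figures rest on assumed falls and assumed rates, and show only why means are a poor instrument with six active subjects.

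The data are collected and no objective is invalidated, so the gap can be closed without touching the conduct of the trial. It should be closed before unblinding, so that the definition precedes the results.

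**What to change.** In Section 10.5:

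1. Define standing minus sitting systolic pressure, diastolic pressure and pulse for each subject at each scheduled time.
2. Summarise the value, and its change from the Day 1 pre-dose set, by dose and for pooled placebo (6 subjects). The pre-dose set is taken within 30 minutes of dosing; screening may be about four weeks earlier.
3. Pre-state a flag for a postural fall. Report the number of subjects who cross it at each time and at any post-dose time, and show whether each had already met it before dosing. The flag is for analysis only and is not a clinical management rule.
4. Say which positions and which statistics the existing change-from-screening summary covers.

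The any-time count needs the placebo column beside it. If a subject crossed the flag by chance on 1% or 5% of occasions, independently (both assumed), the chance of at least one crossing in 13 would be 1 − 0.99^13 = 12% or 1 − 0.95^13 = 49%.

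The cost is wording, one more derived variable and one more table. No assessment is added and no procedure changes.
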